## Background

MicroPort Orthopedics, Inc. (MPO) and the site(s) would like to coordinate the collection of clinical data that may be used for regulatory and research purposes. The specific data to be collected is in the "Data Collection and Parameters." The site(s) will provide MPO with anonymized, de-identified data as requested, understanding the site's overriding obligations about patient care and patient confidentiality.

## Synopsis

Study Title	Evolution NitrX Observational Study	
Study Rationale	To evaluate the safety and performance of Evolution NitrX TKA	
Study Design	Single Center observational study	
Study Sites	[name] (PI)	
Sample Size	100	
Visit Schedule	subject schedule will consist of the following time points:	
Study Timeline	3 yr follow up within 2025 5 yr follow up within 2027 7 years follow up 2029 10 years follow up 2032	
Inclusion Criteria	

Subjects > 18 years of age at the time of surgery

Subjects who were implanted with the Evolution NitrX SKU #'s listed below) in MicroPort Orthopedics' intended patient population listed within the Instructions for Use (IFU).

Willing and able to participate in the clinical study

	
Exclusion Criteria	

Subjects without follow-up history

Subjects not meeting the inclusion criteria

Contraindications as listed in the IFU

Currently enrolled in another study that could affect the endpoints of this protocol.

Has a medical or mental health condition, as judged by the investigator, that would affect the endpoints of this protocol.

	
	Objectives	Outcome Measures
Primary	Survivorship (KM)	Kaplan Meier survival rates at each time point
Secondary	PROMS	KOOS Jr
	SAE including Revisions	Track revisions and reason for revisions throughout the study

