## **Data Collection and Parameters**

### **Data Collection Plan**

- 100 cases with min 10-year follow-up, implanted with Evolution NitrX, will be included in this study.
- Data collection will be prospective.
- Patient preop and intra-op information has been collected in study 20K001, and this study is a continuation of that study.
- Information regarding adverse events or revisions after surgery will be obtained from patient charts.
- IRB will be notified of the change in study collection.
- Site will ensure Informed consent does not need to be re-consented and will consult the IRB.
- Subjects will be called or have an office visit,
  - Has undergone index procedure on the operative knee with NitrX and
  - In the 20K001 study and
  - Would be willing to complete a KOOS Jr survey
- Once the survey/questionnaire is completed, the site will compile the data parameters into a data collection form provided by the MPO and send it to the MPO upon completion for analysis.

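### Does the investigator-judged health exclusion need a reference date, given that subjects enter this study after implantation?

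*Protocol*

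**What the plan says.** The Protocol's Synopsis lists the exclusion as a subject who "Has a medical or mental health condition, as judged by the investigator, that would affect the endpoints of this protocol". Neither the Synopsis nor any other section says when the judgement is made. The age criterion in the same table is dated: "18 years of age at the time of surgery".

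Several statements show that implantation comes before entry:

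- The inclusion criteria take "Subjects who were implanted with the Evolution NitrX" components.
- The exclusion criteria remove "Subjects without follow-up history".
- The Data Collection Plan states: "Patient preop and intra-op information has been collected in study 20K001, and this study is a continuation of that study".
- The Study Timeline starts with "3 yr follow up within 2025", and the Data Collection and Follow-up Schedule has no visit before year 3.

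The primary outcome is Kaplan-Meier survivorship at each time point. KOOS Jr and serious adverse events including revisions are secondary.

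**The concern.** An exclusion that refers to the endpoints and has no date can be read as applying on the day a subject enters. By then roughly three post-operative years may have passed. A complication of the study knee is, literally, a medical condition that affects survivorship, KOOS Jr and adverse events. If an investigator used the rule to leave such a knee out, the cohort would be selected on its own outcome and survivorship would be biased upward.

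The neighbouring criteria do not settle the date. "Contraindications as listed in the IFU" concerns suitability for the implant, and enrolment in another study could be judged before or after surgery.

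The loss might also go unseen. Subject numbering and chart capture are described for study subjects only, so a knee left out at entry need not appear in the data sent to the sponsor. An analysis plan could not recover it.

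**Working it through.** **Time between surgery and entry.** Subtracting the follow-up year from the calendar year in the Study Timeline gives 2025 − 3, 2027 − 5, 2029 − 7 and 2032 − 10. All four equal 2022. Surgery was therefore around 2022, with up to about three years before the first scheduled collection. The premise of the concern is correct.

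**What would have to happen for bias.** Two things are needed: the criterion must be applied again at entry, and it must be applied to conditions related to the revision risk of the study knee.

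- *Re-application.* The Data Collection Plan gives three conditions for contacting a subject: an index procedure with NitrX, membership of 20K001, and "Would be willing to complete a KOOS Jr survey". None is a health screen. The same list has the IRB notified of a change in data collection and expects that consent need not be repeated. That describes an existing cohort carried forward, not new recruitment.
- *Application to the study knee.* The Synopsis sets out to track revisions and their causes. The Postoperatively section collects revision status, reason, date and components. Removing a knee because it is failing would defeat those objectives. The ordinary meaning of the criterion is unrelated illness that would distort the endpoints.

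**Size of the effect.** The Protocol states no revision rate and no expected number of exclusions, so the following is illustrative. The cohort is 100 (from the Synopsis). Assume R revisions by year 10 with R = 3, 6 or 10, no censoring, and a removed knee whose own chance of revision by then is p.

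- Survivorship before removal: 1 − R/100.
- Survivorship after removing one knee: 1 − (R − p)/99.
- Difference: R/100 − (R − p)/99 = (100p − R)/9900, that is (100p − R)/99 percentage points.

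| p | R = 3 | R = 6 | R = 10 |
|---|---|---|---|
| 1 | 97/99 = +0.98 | 94/99 = +0.95 | 90/99 = +0.91 |
| 0.5 | 47/99 = +0.47 | 44/99 = +0.44 | 40/99 = +0.40 |
| 0 | −3/99 = −0.03 | −6/99 = −0.06 | −10/99 = −0.10 |

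The sign changes at p = R/100. Removing a knee with average risk changes nothing, and removing one with lower risk lowers the estimate slightly.

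**Several knees at once.** If 5 of 100 were revised before entry and 2 of those were left out, survivorship would go from 95.0% to 1 − 3/98 = 96.9%. With 8 revised and 4 left out, it would go from 92.0% to 1 − 4/96 = 95.8%. These cases need repeated use of the strained reading.

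**Against sampling error.** Exact (Clopper-Pearson) 95% intervals are 91.5 to 99.4% for 97/100, 87.4 to 97.8% for 94/100, and 82.4 to 95.1% for 90/100. A shift of about 1 point from one knee is small beside any of these.

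**The case for a change.** The best argument for a change is that eligibility belongs in the protocol, the authors dated a criterion when they wished to, and the present tense of this one allows judgement at entry. The decision rests on one investigator's discretion, and no log of 20K001 cases left behind is required. Confidence intervals cover sampling error, not selection, and exclusions of failing knees would all push survivorship the same way. The data may be used for regulatory purposes, and one sentence would close the gap.

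Most of this stands as a description of the wording. The date is missing, selection bias is not covered by the interval, and a clarifying sentence would cost little. What does not stand is the step from ambiguous wording to a wrong result. Nothing in the Protocol shows that the criterion is to be re-applied. If 20K001 applied it before surgery and it is not repeated, the issue disappears; that study's protocol is not at hand, so this cannot be settled either way. A carry-over log is good reporting practice, but its absence is not an error.

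The gain from dating this one criterion would also be limited. The requirement for follow-up history and the willingness to complete KOOS Jr make entry depend on post-operative status or response without any strained reading, and both would remain.

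**Conclusion.** The wording leaves the reference date open, and subjects do enter after implantation. Even so, no change to the plan follows. Upward bias requires an investigator to treat a failing study knee as a disqualifying health condition in a study whose purpose is to record such failures. On the likelier reading, unrelated illness, the direction of any effect is undetermined.

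Under the assumed 3 to 10 revisions per 100, a single removed knee shifts survivorship by between −0.10 and +0.98 points. The actual size cannot be derived from the Protocol, because it gives neither a revision rate nor a number of exclusions. The conclusion rests on the cohort being carried over from 20K001 as the Data Collection Plan describes, and on sites giving the criterion its ordinary meaning. It would need another look if subjects were in fact re-screened at year 3 and excluded for problems of the study knee.

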## Scope

Both MPO and the site(s) agree that the site shall be the sole owner of the data and all intellectual property rights in such data. The site will grant MPO the ability to use the aggregated and/or anonymized data for regulatory and research. The opportunity for MPO and the site(s) to collaborate on further use of the data for publication or abstract submissions for medical or professional conferences may be pursued later.

## Site Responsibility

The site will maintain strict confidentiality regarding any data about subjects. It will control the subjects' data as defined in relevant data protection laws or regulations applicable to the site.

The site will be responsible for obtaining approvals from an Institutional Review Board (IRB) for data collection. The site will be the sole owner of the data and all related intellectual property rights. However, the site will grant MPO the ability to use, edit, compile, and disseminate the data for regulatory and research activities. The site will not disclose any patient-identifiable information to MPO. The site will provide data on patients solely in aggregated and/or anonymized form, preventing MPO from identifying individual patients.

## **Data Collection and Parameters**

### **Data Collection Plan**

- 100 cases with min 10-year follow-up, implanted with Evolution NitrX, will be included in this study.
- Data collection will be prospective.
- Patient preop and intra-op information has been collected in study 20K001, and this study is a continuation of that study.
- Information regarding adverse events or revisions after surgery will be obtained from patient charts.
- IRB will be notified of the change in study collection.
- Site will ensure Informed consent does not need to be re-consented and will consult the IRB.
- Subjects will be called or have an office visit,
  - Has undergone index procedure on the operative knee with NitrX and
  - In the 20K001 study and
  - Would be willing to complete a KOOS Jr survey
- Once the survey/questionnaire is completed, the site will compile the data parameters into a data collection form provided by the MPO and send it to the MPO upon completion for analysis.

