### **De-Identified Subject #**

- A minimum of 100 subjects with Evolution NitrX will be assigned a de-identified subject number entered into the case report form.

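### The size is stated as 100 cases with at least 10 years of follow-up, a count that prospective follow-up of 100 subjects would not be expected to deliver

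*Protocol*

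**What the plan says.** The Data Collection Plan opens with the size: "100 cases with min 10-year follow-up, implanted with Evolution NitrX, will be included in this study". It then says "Data collection will be prospective" and describes the source of the cases: "Patient preop and intra-op information has been collected in study 20K001, and this study is a continuation of that study". The Synopsis gives the sample size as 100 with no follow-up condition. Its only eligibility criterion that touches on follow-up is the exclusion "Subjects without follow-up history".

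The primary outcome in the Synopsis is "Kaplan Meier survival rates at each time point". The Data Collection and Follow-up Schedule has contacts at 3, 5, 7 and 10 years. The Postoperatively section records death and its date, and revision and its date. Between contacts the charts also serve as a source: "Information regarding adverse events or revisions after surgery will be obtained from patient charts".

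The Study Timeline in the Synopsis fixes the contacts by calendar year: "3 yr follow up within 2025 5 yr follow up within 2027 7 years follow up 2029 10 years follow up 2032". No surgery dates are given.

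**The concern.** A study fixes how many cases it enters. It does not fix how many of them will still be under observation ten years after surgery. The Data Collection Plan puts the second quantity where the first belongs, and nothing else in the protocol bridges the two: there is no larger starting number and no attrition allowance.

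Two things follow. The stated count of 10-year cases is more favourable than the design would be expected to give, which matters for data that may be used for regulatory purposes (Background). Also, because the sentence says which cases are included, a literal reader could apply it as a selection rule. Unrevised cases that die or are lost before year 10 would then leave the analysis, although Kaplan-Meier should keep them at risk until they are censored. Dropping them while keeping revised cases would overstate failure. Dropping early-revised cases too, as lacking ten years on the implant, would remove the events themselves.

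The calendar entry for the last contact raises a related, smaller question: whether a case that completes the schedule has been observed to 10.0 years, the last primary time point.

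**Working it through.** **1. The plan's own figure.** The protocol states 100 and gives no precision target, event rate, power or attrition rate. There is no calculation to reproduce, and no stated arithmetic is wrong. The check is whether the count described can come out of the design described.

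**2. The sections side by side.** Collection is prospective and the schedule starts at year 3, so on the Synopsis calendar no case has ten years when it enters. Eligibility contains no ten-year condition. Death is a recorded status. The number reaching year 10 is thus unknown at entry and can only be equal to or below the number entered.

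**3. Attrition (all rates assumed).** For a cumulative loss *d* by year 10, 100 × (1 − *d*) cases remain and 100/(1 − *d*), rounded up, must start for 100 to remain.

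| *d* | Remaining of 100 | Needed at start |
|---|---|---|
| 5% | 95 | 106 |
| 10% | 90 | 112 |
| 20% | 80 | 125 |
| 30% | 70 | 143 |

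With independent losses, the chance that all 100 reach year 10 is (1 − *d*)^100: 0.99^100 = 37% and 0.95^100 = 0.6%.

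Expressed as an annual rate *a*:

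| *a* | From year 3: (1 − *a*)^7 | From surgery: (1 − *a*)^10 |
|---|---|---|
| 1% | 0.932 | 0.904 |
| 2% | 0.868 | 0.817 |
| 4% | 0.751 | 0.665 |
| 7% | 0.602 | 0.484 |

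**4. Calendar.** 2025 − 3, 2027 − 5, 2029 − 7 and 2032 − 10 all equal 2022, so the timeline implies surgery in 2022. The shortest follow-up at a 2032 contact is from 31 December 2022 to 1 January 2032, 9.0 years. The longest is from 1 January 2022 to 31 December 2032, 11.0 years.

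Let *s* be the surgery date within 2022 and *c* the contact date within 2032, each as a fraction of the year, independent, with *s* uniform. Then P(*c* < *s*) = 1 − E[*c*]:

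- contacts even over 2032: 1 − 0.5 = 50%, short by 4.0 months on average;
- all in the first quarter: 1 − 0.125 = 87.5%, short by 5.3 months;
- all in the fourth quarter: 1 − 0.875 = 12.5%, short by 1.0 month.

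If surgery was in 2021 or earlier, every 2032 contact is at 10 years or later, but the 2025 contact then averages about 4 years or more instead of 3. If it was in 2023, every 2032 contact is before the anniversary.

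**5. Cost in precision.** The Greenwood variance of the log survival estimate is ∫₀¹⁰ *r* / (*n* G(*t*) S(*t*)) d*t*, with *n* = 100, *r* = −ln(0.94)/10 (assumed 94% survivorship at 10 years, constant hazard), S(*t*) = exp(−*rt*), and G(*t*) = (1 − *a*)^(*t* − 3) after year 3. Early contacts multiply G(*t*) between years 9 and 10 by the probability that the contact has not yet occurred, which is 1 − (*t* − 9)²/2 for even contacts. The standard error of the 10-year rate is 0.94 times the square root of the integral. Ratios are against no early contact:

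| *a* | Even over 2032 | All in first quarter |
|---|---|---|
| 1% | 1.013 | 1.063 |
| 2% | 1.014 | 1.066 |
| 4% | 1.015 | 1.071 |
| 7% | 1.017 | 1.081 |

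At *a* = 1% the standard error moves from 2.41 to 2.44 percentage points with even contacts.

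**The case against.** The strongest reply is that the surrounding text already settles the meaning. The sentence sits in a data collection plan, collection is prospective, eligibility asks for no ten years, contacts start at year 3, and deaths feed a Kaplan-Meier analysis that tolerates incomplete follow-up. A rule requiring ten completed years would make the 3-, 5- and 7-year rates pointless. This stands: planned duration is the likelier meaning. A reader might infer that the protocol selects on ten-year follow-up and that its survivorship will be biased. The documents do not support that; the bias is a risk only if the sentence is applied as written.

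It is also fair that no precision target or decision rule rests on 100 at risk at year 10, and that every attrition rate above is assumed. A reader might infer a sample-size error or a study that is too small, but nothing in the protocol lets that be shown. The subject-numbering section says "A minimum of 100 subjects with Evolution NitrX will be assigned a de-identified subject number", so 100 is not a cap. That difference in wording is clerical and is no part of this point. Detailed censoring rules may properly sit in an SAP that is not at hand.

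On the calendar, the surgery year is inferred, nothing instructs an early contact, and a site would normally schedule from the surgery date, so independence of the two dates is pessimistic. Chart review can also supply revision information after the contact. A reader might infer that half the cohort goes unobserved at year 10. That holds only under those assumptions and on contact data alone. What remains is that the entry permits an early last contact and the follow-up schedule does not rule it out.

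**Conclusion.** The point holds as a minor correction of wording. The Data Collection Plan states as the size a count of 10-year cases that following 100 subjects prospectively, with recorded deaths and no attrition allowance, would not be expected to give. That conclusion needs only some attrition over the decade; how far short the count falls depends on rates the protocol does not give. The sentence most likely describes planned duration, but it does not say so, and read literally it conflicts with the primary outcome.

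The calendar point is secondary and low in impact. It rests on surgery in 2022, which all four timeline entries imply. It costs about 1.3% to 1.7% of the standard error if contacts are even over 2032 and independent of surgery date, and about 6% to 8% if all fall in the first quarter. It would cost less where charts carry later information. It does not invalidate the 10-year estimate.

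**What to change.** In the Data Collection Plan, restate the size along these lines: *100 NitrX cases from 20K001 will be enrolled, with planned follow-up to 10 years; all enrolled cases are included whatever their achieved follow-up.* Leave the detailed censoring rules to the SAP.

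In the Synopsis timeline and the follow-up schedule, set the 10-year data-collection contact on or after each subject's surgery anniversary instead of by calendar year alone.

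The cost is protocol wording, with no extra patients. The protocol would no longer promise 100 cases at ten years, and a few final contacts for late-2022 surgeries may fall in 2033.

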### **Data Collection and Follow-up Schedule**

Data Collection	3 years	5 years	7 years	10 years
KOOS Jr	X	X	X	X
SAE including Revision	X	X	X	X

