## Postoperatively

- Subject Status
  - Is the subject deceased?
  - Date the subject was deceased.
- Is the subject revised?
  - Reasons for revision
  - If a revision occurs, the removed and retained components will be provided.
  - Date that the revision occurred.
- Adverse events
  - Information regarding adverse events that have occurred after surgery will be provided.

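### Charts at one centre are the only named source of revisions and SAEs over 10 years, so revisions done elsewhere may be missed and survivorship overstated

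*Protocol*

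**What the plan says.** Under Data Collection Plan, the Protocol states: "Information regarding adverse events or revisions after surgery will be obtained from patient charts". No other sentence names a source for these events. The related places are:

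- **Synopsis.** The design is a "Single Center observational study". The primary outcome measure is "Kaplan Meier survival rates at each time point", with follow-up at 3, 5, 7 and 10 years, the last in 2032. SAEs, including revisions, are a secondary outcome.
- **Data Collection Plan, subject contact.** "Subjects will be called or have an office visit", so an office visit is not required. The only activity mentioned with this contact is the questionnaire: "Would be willing to complete a KOOS Jr survey". That line is one of the conditions for being contacted, not a script for the call.
- **Data Collection and Follow-up Schedule.** "SAE including Revision" is marked at all four time points, with no source given.
- **Postoperatively.** The items to record include "Is the subject revised", with date, reasons and components. Again no source is given.

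**The concern.** A chart at the implanting centre reliably shows what that centre did or was told. Over 10 years some subjects may have a knee revised at another hospital, and a subject followed only by telephone gives the site no clinical occasion to notice it. A site that follows the Data Collection Plan to the letter could review its own charts, find nothing, and record the knee as unrevised without departing from the Protocol.

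Revision is the event in the primary analysis. A missed revision removes a downward step from the Kaplan-Meier curve and keeps the knee in the risk set, so the error has one direction, in favour of the device. The SAE outcome has the same gap. The Background section says the data may be used for regulatory purposes. An analysis plan cannot repair this, because the events would never have been collected.

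**Working it through.** The Protocol states no expected survivorship, revision rate or basis for the sample size, so there is no figure of its own to reproduce. The check has two parts: what the text requires, and how large the effect could be.

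**What the text requires**

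| Place in the Protocol | What it fixes | Source of event data |
|---|---|---|
| Synopsis | Kaplan-Meier survivorship; SAEs including revisions | none stated |
| Data Collection Plan | events taken from charts; contact by call or visit | patient charts |
| Data Collection and Follow-up Schedule | SAE and revision at 3, 5, 7 and 10 years | none stated |
| Postoperatively | revision status, date, reasons, components; adverse events | none stated |

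None of these places requires a question about care elsewhere, a request for outside records or a registry check.

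**How large the effect could be**

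Inputs:
- *n* = 100 cases (Synopsis; Data Collection Plan).
- *S*, true 10-year survivorship: assumed to be 97%, 95% or 90%.
- *m*, share of revisions done elsewhere and not charted: assumed to be 10% to 40%.
- Censoring is ignored, and each revision is taken to be missed independently.

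Expected observed survivorship = 1 − (1 − *m*)(1 − *S*).

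| True *S* | *m* = 10% | *m* = 40% |
|---|---|---|
| 97% | 1 − 0.9 × 0.03 = 97.3% | 1 − 0.6 × 0.03 = 98.2% |
| 95% | 1 − 0.9 × 0.05 = 95.5% | 1 − 0.6 × 0.05 = 97.0% |
| 90% | 1 − 0.9 × 0.10 = 91.0% | 1 − 0.6 × 0.10 = 94.0% |

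At *S* = 95% there are 5 true revisions in 100 cases:
- Expected number missed = 5*m*: 0.5 at *m* = 10% and 2.0 at *m* = 40%.
- Chance of missing at least one = 1 − (1 − *m*)^5: 1 − 0.9^5 = 41%, and 1 − 0.6^5 = 92%. At 20% and 30% it is 67% and 83%.

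Exact (Clopper-Pearson) 95% intervals for survivorship with *n* = 100:
- 5 revisions counted: 88.7% to 98.4%.
- 3 revisions counted (2 of the 5 missed): 91.5% to 99.4%.

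In that last case the point estimate moves by 2 points, against an interval 98.4 − 88.7 = 9.7 points wide.

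**The case against.** The strongest reply is that the finding rests largely on silence. The Protocol does not say charts are the *only* source. Collection is described as prospective, the schedule puts SAEs and revisions in the same grid and at the same time points as KOOS Jr, and the postoperative items are worded as status questions. The site also compiles its form after the questionnaire is completed, which links event status to the contact. Charts can hold outside correspondence. The data collection form and the parent study 20K001, neither of which is shown, may contain the missing question. The size is assumed throughout, nothing in the Protocol anchors the 40% end, and no performance threshold is stated that a shift of this size could cross.

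Much of this is fair. The text does not forbid asking the subject, a site may well do so, and the size cannot be established from the document. But these points show only that asking is possible. The one sentence that assigns a source assigns charts, and nothing obliges the site to obtain outside records. That the shift is smaller than the sampling error does not dispose of it either, because the interval covers chance and not a one-sided loss of events.

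Two practical objections also stand in part. Recall of SAEs over intervals of two to three years is weak, and asking subjects does nothing for those who are not reached.

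**Conclusion.** The concern holds and should be fixed; confidence is moderate. What is certain from the text is that charts are the only named source, that the study is single-centre with 10-year follow-up, and that subjects are not required to be asked about events elsewhere. The direction is also certain: a missed revision can only raise the survivorship estimate. The size is not known. Under the assumed 10% to 40% of revisions uncharted, the overstatement is 0.3 to 1.2 points at a true 97%, 0.5 to 2.0 points at 95% and 1.0 to 4.0 points at 90%. This is a weakness in how events are ascertained. It does not show that events will in fact be lost.

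**What to change.** Reword the sentence in the Data Collection Plan so that revision and SAE status is obtained by asking every subject, at each planned 3-, 5-, 7- and 10-year call or visit, about any revision or reoperation of the index knee and any SAE at any hospital, with date and reason. Charts or outside records then confirm the report and supply the removed and retained components. For subjects not reached, whom this change does not help, the form could carry the last date on which implant status was confirmed, so that they need not be counted as unrevised by default.

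The cost is a few questions at a contact already planned, and a records request when an outside event is reported. No extra visits are needed. The Protocol already foresees that "IRB will be notified of the change in study collection" and that the site will check with the IRB whether re-consent is needed. The added questions, and any patient authorisation for outside records, should go into that same exchange. The change is best made early, since events not asked about at one time point may not be fully recoverable later.

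### The only stated step for sending revision and death data follows a completed KOOS Jr, so read literally the Kaplan-Meier primary outcome depends on response to a secondary questionnaire

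*Protocol*

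**What the plan says.** - **Primary outcome** (Protocol, Synopsis): "Kaplan Meier survival rates at each time point". KOOS Jr is a secondary outcome.
- **Source of events** (Data Collection Plan): "Information regarding adverse events or revisions after surgery will be obtained from patient charts". This sentence carries no survey condition.
- **Who is contacted** (same list): subjects are called or seen if they had the index procedure with NitrX, were in study 20K001, and "Would be willing to complete a KOOS Jr survey". The three conditions are joined by "and".
- **When data are sent** (last item of the same list): "Once the survey/questionnaire is completed, the site will compile the data parameters into a data collection form provided by the MPO", after which the form goes to the sponsor. No other transfer step is given.
- **What the form carries** (Postoperatively): death and its date, revision with its date, reasons and components, and adverse events.
- **When** (Data Collection and Follow-up Schedule): KOOS Jr and SAE/revision are separate rows, both at 3, 5, 7 and 10 years. The Synopsis timeline begins with "3 yr follow up within 2025".
- **Eligibility** (Synopsis): "Willing and able to participate in the clinical study". KOOS Jr is not mentioned among the criteria.

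**The concern.** A revision recorded in the chart is known to the site whether or not the patient returns a questionnaire. The Data Collection Plan nevertheless makes the questionnaire the trigger for the form that carries the revision. A site following the list step by step has no instruction to send anything for a non-responder. For a deceased subject the steps cannot be carried out at all: the form asks for a date of death, but its trigger is a survey that this subject cannot complete. Charts are named as the source for adverse events and revisions, and no source is named for deaths.

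This matters because Kaplan-Meier censoring works only on records that reach the analyst. If revised patients respond less often than others, survivorship comes out too high; if they respond more often, too low. A statistical analysis plan can set censoring rules, but it cannot supply records that the data flow never delivered. With 100 cases few revisions are likely, so each one not sent counts.

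**Working it through.** The Protocol gives no expected survivorship, response rate or mortality, so there is no figure of its own to reproduce. Every rate below is an assumption, and the results only illustrate size.

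**1. The steps side by side**

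| Case at a scheduled visit | Revision known from chart? | Survey completed? | Stated route to the sponsor |
|---|---|---|---|
| Responds | yes | yes | yes |
| Declines or cannot be reached | yes, if charted | no | none stated |
| Deceased | yes, if charted | impossible | none stated, though death date is a listed item |

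**2. One revised case not sent.** Take 100 cases with 5 revisions (true survivorship 95%). If m revised cases never reach the sponsor, the crude estimate is 1 − (5 − m)/(100 − m):
- m = 1: 1 − 4/99 = 96.0%
- m = 2: 1 − 3/98 = 96.9%
- m = 3: 1 − 2/97 = 97.9%

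**3. Single-survey illustration, no censoring.** Let r be the 10-year revision risk, and q1 and q0 the response of revised and unrevised cases. Apparent survivorship is 1 − r·q1 / [r·q1 + (1 − r)·q0].
- r = 5%, q0 = q1 = 80%: 1 − 0.040/0.800 = 95.0% (no bias)
- r = 5%, q0 = 80%, q1 = 60%: 1 − 0.030/0.790 = 96.2%
- r = 5%, q0 = 80%, q1 = 40%: 1 − 0.020/0.780 = 97.4%
- At 80%/40% with other risks: 98.5% against a true 97% (r = 3%), and 94.7% against a true 90% (r = 10%)

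**4. Survey trigger applied at all four visits (simulation).** Revision times are exponential with 10-year survivorship 95%. Visits are at 3, 5, 7 and 10 years, with independent response at each. A case enters if any survey is completed. A revision counts only if a survey is completed at or after it; otherwise the case is censored at its last survey. Unrevised cases answer 85% of visits.

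| Revised cases answer | 10-year estimate, no deaths | With 2% annual mortality |
|---|---|---|
| 100% | 94.7% | 94.7% |
| 85% | 95.0% | 95.0% |
| 70% | 95.3% | 95.4% |
| 50% | 96.0% | 96.1% |
| 20% | 97.9% | 97.9% |

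The bias is smaller than in step 3 for a similar gap, because a revised case has several later visits at which it may still be reported.

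**5. Deaths.** At 1%, 2% or 3% a year, 1 − (1 − a)^3 gives about 3, 6 or 9 deaths per 100 before the first survey, and 1 − (1 − a)^10 gives about 10, 18 or 26 by year 10. On a literal reading none of those dates would be sent. The last column of the table shows that this alone hardly changes the estimate.

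**6. Precision when response is unrelated to revision.** The exact 95% interval is 88.7–98.4% for 5 revisions in 100, and 87.7–98.6% for 4 in 80. Only a little precision is lost.

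**The case against.** The strongest reply is that the survey sentence describes the order of work, not a filter. Revisions are chart-based, the schedule lists SAE/revision on its own row, and the form asks whether the subject is deceased, so its drafters had such cases in mind. That is a fair reading. It is not the only one, and the text gives a site no instruction that favours it.

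Several stronger readings are tempting, and the documents do not support them:
- **Non-responders drop out with their events.** No sentence says so. It is inferred from the sequence; what can be said is that no route is stated.
- **KOOS Jr willingness is an entry criterion, so early failures are selected out.** The condition governs contact. Eligibility in the Synopsis asks only for willingness to take part, and the study is called a continuation of 20K001 in which re-consent is expected to be unnecessary. The form asks for the revision date, so a first form at year 3 can still record an earlier revision.
- **The sponsor could never recover missing cases.** That depends on what was collected and shared under 20K001, which is not shown.
- **Only cases that complete 10 years are analysed.** "100 cases with min 10-year follow-up, implanted with Evolution NitrX, will be included in this study" could suggest this, but with prospective collection at four visits it reads as planned duration. The exclusion "Subjects without follow-up history" is harmless alone, since a case with no follow-up adds no person-time.
- **Missing deaths distort survivorship.** Step 5 shows little effect.

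Two further objections stand. A modest response gap (85% against 70%) moves the estimate by about 0.35 points, small against the sampling interval. And charts at a single center can miss revisions done elsewhere: if 20% of 5 revisions were missed and those cases counted as event-free, the estimate would be 1 − 4/100 = 96.0%, a similar error. Chart data alone therefore do not guarantee an unbiased result.

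**Conclusion.** The point holds as a conflict in the stated data flow. The chart, contact and transfer sentences of the Data Collection Plan do not fit together, and the transfer sentence does not fit the death item under Postoperatively. Followed literally, the primary outcome depends on response to a secondary questionnaire.

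The consequence is conditional. There is no bias if response is unrelated to revision, and the direction is unknown if it is related. Under the assumptions of step 4 the error runs from about 0.3 points downward (revised cases answer every visit) to about 1 point upward (they answer half) and nearly 3 points upward (they answer one visit in five). The last needs a very large response gap. The death dates are a matter of consistency, not of material bias. It is worth correcting because it touches the only primary outcome and the correction is cheap; it does not show that the study will report wrong survivorship.

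**What to change.** In the Data Collection Plan, replace the transfer step with wording such as:

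> At 3, 5, 7 and 10 years the site completes and sends the data form for every enrolled 20K001 case implanted with Evolution NitrX, whether or not a KOOS Jr is returned, using the chart and any contact made. The form records revision and its date, death and its date, and the date on which status was last known. Cases without revision are censored at that last date.

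In addition:
- Limit the willingness condition to the KOOS Jr itself.
- Ask the IRB, already to be consulted on consent, to confirm that 20K001 consent covers sending data on cases that are not reached.
- Report how many 20K001 cases were not entered, and why.
- Count a case as event-free only up to the last date on which that is known, because a chart may miss a revision done elsewhere.

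Cost: no added visits or surveys, some extra chart review and form completion for non-responders, one question to the IRB, and a few changes of wording. This reduces the dependence on survey response but does not remove the risk of revisions unknown to the site.
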